## 18.27 Short Form (36) Health Survey (SF-36)

The SF-36® Health Survey (acute Version 2) consists of 36 questions that will be scored and grouped into 8 health domains as well as one psychometrically-based PCS score and one MCS score. The calculations of the health domain scores and the PCS and MCS scores will be done

using the QualityMetric Health Outcomes™ Scoring Software 5.0, Version 5.0.6163.22119 using the 2009 US Norm as well as “Maximum Data Recovery” as missing data estimation method.

The 8 health domains are:

- Physical functioning (PF)
- Role-physical (RP)
- Bodily pain (BP)
- General health (GH)
- Vitality (VT)
- Social functioning (SF)
- Role-emotional (RE)
- Mental health (MH)

For each health domain score and PCS and MCS scores, the change from baseline is defined as:

$$\text{Domain score at specific time point} - \text{domain score at baseline}$$

## 18.28 EuroQol 5 dimensions 5 levels (EQ-5D-5L)

5 dimensions: The EQ-5D-5L consists of 5 dimensions (mobility, self-care, usual activities, pain/discomfort, anxiety/depression) each of which can take one of 5 responses. The responses record 5 levels of severity (no problems/slight problems/moderate problems/severe problems/extreme problems) within a particular EQ-5D dimension, coded as 1 to 5.

For each dimension, the change from baseline is defined as:

$$\text{Dimension score at specific time point} - \text{dimension score at baseline}$$

If the score at either of the time points is missing, no change from baseline will be calculated.

Index value: The descriptive system can be represented as a health state, e.g. health state 21143 represents a patient who indicates slight problems on the mobility dimension, no problems on the self-care and usual activities dimensions, severe pain or discomfort, and moderate problems on the anxiety/depression dimension. These health states will be converted to a single index value using the existing value sets for the US.

VAS: The patients will record their self-rated health on a 0 to 100 VAS. The change from baseline is defined as:

$$\text{VAS at specific time point} - \text{VAS at baseline}$$

If the VAS assessment at either of the time points is missing, no change from baseline will be calculated.

## 18.29 Work productivity and activity impairment:specific health problems (WPAI:SHP)

The WPAI:SHP contains questions related to the patients quantitative assessment of the amount of absenteeism, presenteeism and daily activity impairment attributable to gout. The questions in the WPAI:SHP records the following:

- Q1 = currently employed
- Q2 = hours missed from work due to specified problem (gout)
- Q3 = hours missed from work due to other reasons
- Q4 = hours actually worked
- Q5 = degree problem affected productivity while working (score 0 to 10)
- Q6 = degree problem affected regular activities (score 0 to 10)

Based on these questions, the percentage of work time missed due to gout, percentage of impairment while working due to gout, percentage of overall work impairment due to gout, percentage of activity impairment due to gout and total work time will be derived. Calculations will only be performed if the patient has responses to all questions involved in a respective formula. If hours worked=0, productivity assessments related to work will not be calculated, only the percentage of activity impairment due to problem.

Currently employed will be set to Yes if Question 1 is answered 'Yes', or if Question 1 is answered 'No' or missing and questions regarding hours missed or worked >0 (Questions 2, 3, and 4).

Percent work time missed due to problem is defined as:

$$\text{Question 2} / (\text{Question 2} + \text{Question 4})$$

Percent impairment while working due to problem is defined as:

$$\text{Question 5} / 10$$

Percent overall work impairment due to problem is defined as:

$$[\text{Question 2} / (\text{Question 2} + \text{Question 4})] + \\ [(1 - (\text{Question 2} / (\text{Question 2} + \text{Question 4})) ) x (\text{Question 5} / 10 ) ]$$

Percent activity impairment due to problem is defined as:

$$\text{Question 6} / 10$$

Total work time is defined as:

$$\text{Question 2} + \text{Question 3} + \text{Question 4}$$

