outpatient visits during the last week will be recorded at Day 8 and Day 15. In addition, the Work Productivity and Activity Impairment Questionnaire V2.0 (WPAI:SHP) will be completed by the patient at the same timepoints. The WPAI is a patient-reported quantitative assessment of the amount of absenteeism, presenteeism and daily activity impairment attributable to general health (WPAI:GH) or a specific health problem (WPAI:SHP). The 6 questions in the WPAI:SHP questionnaire for gout are; employment status (yes/no), work hours missed due to gout, work hours missed due to any other reason, hours of actual working, productivity while were working (0-10 scale; gout had no effect on my work/gout completely prevented me from working) and a global measure of activity impairment (1-10, gout had no effect on my daily activities/gout completely prevented me from doing my daily activities) (42). WPAI:SHP has a recall period defined as “past 7 days not including today”.

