9.3.5.3 WPAI:SHP

Based on the WPAI:SHP the following scores will be calculated for Day 8 and Day 15; percent work time missed due to gout, percent impairment while working due to gout, percent overall work impairment due to gout and percent activity impairment due to gout.

The WPAI:SHP scores at Day 8 and Day 15 for the first flare and subsequent flares will be presented by descriptive statistics.

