## **5 Changes from protocol affecting the statistical analysis**

According to the protocol, AEs and SAEs will be classified as occurring during ADA presence when the starting date for the AE is within the time period after the latest negative assessment until next negative assessment with a positive assessment of ADA in between. Instead AEs and SAEs will be presented by ADA positive and ADA negative patients for the whole study period.

The relationship between ADA and efficacy and the relationship between ADA and IL-Ra/anakinra concentrations over time will also be explored which was not described in the protocol.

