### **17.3 Work productivity and activity impairment:specific health problems (WPAI:SHP)**

Based on the WPAI:SHP the following scores will be calculated for Day 8 and Day 15; percent and actual work time missed due to gout, percent impairment while working due to gout, percent overall work impairment due to gout, percent activity impairment due to gout and in addition total work time will be calculated (see Section 18.29).

The WPAI:SHP scores at Day 8 and Day 15 for the first flare and subsequent flares will be presented by descriptive statistics.

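### SAP 18.29 leaves work-loss scores blank when hours worked are 0, although its own formulas give 100% for a patient with gout-related hours missed (exploratory endpoint)

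*SAP*

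**What the plan says.** SAP 18.29 defines three work-related percentages and one for daily activities:

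- Percent work time missed: Q2/(Q2+Q4).
- Percent impairment while working: Q5/10.
- Percent overall work impairment: Q2/(Q2+Q4) + [1 − Q2/(Q2+Q4)] × Q5/10.
- Percent activity impairment: Q6/10.

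It also defines total work time as Q2+Q3+Q4, where Q3 is hours missed for other reasons.

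Two rules limit the calculation. The first is a completeness rule: "Calculations will only be performed if the patient has responses to all questions involved in a respective formula". The second concerns patients who did no work: "If hours worked=0, productivity assessments related to work will not be calculated, only the percentage of activity impairment due to problem".

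Protocol 9.3.5.3 lists the scores to be derived ("percent work time missed due to gout, percent impairment while working due to gout, percent overall work impairment due to gout", plus activity impairment) without giving formulas or item rules. SAP 17.3 adds actual work time missed and total work time, and sets the analysis: "The WPAI:SHP scores at Day 8 and Day 15 for the first flare and subsequent flares will be presented by descriptive statistics".

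**The concern.** A patient who reports hours missed for gout and no hours worked has the largest work loss the questionnaire can record. The zero-hours rule gives that patient no work score, although the formulas in the same section return a valid one. Whether the score is missing then depends on its value: the patients removed are those at the maximum.

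Protocol 7.5.8.1 gives the questionnaire a recall of the past 7 days, not counting the current day. The Day 8 score therefore covers roughly Days 1–7 of the flare, which include the five treatment days, and complete absence from work is plausible then. If such patients are left out, the tables understate work loss in every arm where they occur and the rest miss less than 100%. They can also hide or exaggerate a difference between arms.

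**Working it through.** **Inputs.** The formulas and both rules are from SAP 18.29. The planned 53 patients per arm is from SAP section 7. The plan states no figure for this point, so there is nothing to reproduce. The rates f and m and the employed share are assumptions, because the documents give none.

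**Step 1: the formulas at and near zero hours worked.**

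| Q2 | Q4 | Work time missed | Overall impairment, Q5 = 0 / 5 / 10 | Under the zero-hours rule |
|---|---|---|---|---|
| 40 | 0 | 40/40 = 100% | 100% / 100% / 100% | withheld |
| 1 | 0 | 1/1 = 100% | 100% / 100% / 100% | withheld |
| 39 | 1 | 39/40 = 97.5% | 97.5% / 98.75% / 100% | kept |
| 0 | 0 | 0/0, undefined | undefined | withheld, correctly |

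At Q4=0 and Q2>0 the Q5 term is multiplied by 1 − 100% = 0, so overall impairment does not depend on Q5. One hour worked decides between a score of at least 97.5% and no score.

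**Step 2: what else blocks the scores.** Percent work time missed does not use Q5, so only the zero-hours rule withholds it. Overall impairment has Q5 in its formula. If a patient who did no work leaves Q5 blank, the completeness rule withholds that score as well, and a correction has to deal with both rules.

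**Step 3: effect on one arm's mean.** Let f be the share of patients with Q2+Q4>0 who have Q4=0, and m the mean score of the rest. The mean over all of them is f×100% + (1−f)m. The reported mean is m, so the shortfall is f(1−m), in percentage points:

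| f | m = 20% | m = 30% | m = 40% |
|---|---|---|---|
| 5% | 4 | 3.5 | 3 |
| 10% | 8 | 7 | 6 |
| 20% | 16 | 14 | 12 |
| 30% | 24 | 21 | 18 |

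Example: f=20%, m=30% gives 20% + 0.8 × 30% = 44%, against 30% reported.

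**Step 4: effect on a difference between two arms** (second minus first).

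| f, arms 1 / 2 | m, arms 1 / 2 | True means | True difference | Reported difference |
|---|---|---|---|---|
| 10% / 30% | 30% / 30% | 37% / 51% | 14 | 0 |
| 10% / 10% | 20% / 40% | 28% / 46% | 18 | 20 |
| 10% / 30% | 20% / 40% | 28% / 58% | 30 | 20 |
| 30% / 10% | 20% / 40% | 44% / 46% | 2 | 20 |

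The error is the difference between the two arms' shortfalls. With f of 10–30% and m of 20–40% in each arm, shortfalls run from 6 to 24, so the error lies between −18 and +18 points.

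**Step 5: number of patients.** If half of 53 are employed (assumed), that is 26.5 per arm; 10–30% of these is 2.7–8.0, or about 3–8 patients per arm.

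**The case against.** The best defence is that this is a stated exception to general formulas. A programmer would know what to do, and the SAP lists a web page for the questionnaire among its references, which cannot be checked here. That is fair as to clarity, but a clear rule that removes patients at the maximum score still biases the mean.

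Other points on that side, and what stands:

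- **The protocol is silent on item rules.** It names the scores without formulas, so the absence of an entry in SAP section 5 does not show an undeclared change. Likewise, the SAP rule that hours missed can mark a patient as employed does not promise a work score. The point needs neither; it rests on the mismatch between rule and formulas.
- **The patient is not wholly lost.** The activity score is kept, and SAP 17.3 promises actual work time missed and total work time. Read literally, though, *only* in the zero-hours rule drops those two as well.
- **Q3 is ignored.** A patient with Q2=2, Q3=38 and Q4=0 would score 100%, although gout accounts for 2 of 40 hours. This is true, but it is how the SAP formula treats Q3 at every value of Q4. It does mean that not every affected patient missed all work because of gout.
- **The rates are assumed.** They are. The 14-point loss needs a threefold difference between arms in complete absence. The 18-point extremes also need the arm with more absence to have half the mean loss among the rest. With equal f and m of 20% versus 40%, the error is 2–6 points.
- **The tier is low.** The scores are exploratory, with no test planned. This limits the priority, not the correctness.

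**Conclusion.** The concern holds. For any patient with Q2>0 and Q4=0, SAP 18.29 withholds two scores that its own formulas put at 100%. Withholding is right only where Q2+Q4=0, and reasonable for impairment while working when no work was done.

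The direction within an arm is certain: the mean is too low by f(1−m) whenever such patients exist and the rest average below 100%. The size is not known from the documents: 6–24 points for assumed f of 10–30% and m of 20–40%, and 3–4 points at f=5%. The direction of any distortion between arms cannot be predicted.

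The rule should be corrected, at low priority, because the endpoint is exploratory and descriptive. The primary and secondary analyses, the sample size and the safety conclusions are unaffected.

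**What to change.** Replace the zero-hours sentence in SAP 18.29 with:

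> If Q4=0 and Q2>0, percent work time missed and percent overall work impairment are set to 100% whether or not Q5 is answered, and percent impairment while working is left missing. If Q2+Q4=0, percent work time missed, percent impairment while working and percent overall work impairment are not calculated. Actual work time missed and total work time (Q2+Q3+Q4) are still reported.

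State that this takes precedence over the completeness rule. Add to the WPAI:SHP table the number of patients with Q2>0 and Q4=0, by arm, visit and flare.

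The cost is one replaced sentence with its precedence statement and one count row, with no new data. SAP 6.2 places the exploratory analyses of all flares in the final analysis and allows documented SAP updates before the final database lock, so the plan has room for the change.

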### **18.30 Health care resource utilization**

At Day 8 and Day 15, patients will be asked about their unscheduled outpatient visits as well as days of hospitalization due to the acute gout flare during the last week. The total number of outpatient visits for Week 1 and Week 2, respectively, is defined as:

*No. visits to a Specialist + No. visits to a Nurse + No. visits to a Family Physician*

The total number of outpatient visits for a flare is defined as:

*Total No. visits for Week 1 + Total No. visits for Week 2*

The total number of days of hospitalization for a flare is defined as:

*Total No. days of hospitalization for Week 1 + Total No. days of hospitalization for Week 2*

